### 10.5.3 Recording and Follow-Up of Adverse Event and/or Serious Adverse Event

AE and SAE Recording

 
• When an AE/SAE occurs, it is the responsibility of the Investigator to review all documentation (eg, hospital progress notes, laboratory reports, and diagnostics reports) related to the event.
 
• The Investigator will then record all relevant AE/SAE information.
 
• It is not acceptable for the Investigator to send photocopies of the participant's medical records to the Sponsor or designee in lieu of completion of the applicable/required report form.
 
• There may be instances when copies of medical records for certain cases are requested by the Sponsor or designee. In this case, all participant identifiers, with the exception of the participant number, will be redacted on the copies of the medical records before submission to the Sponsor or designee.
 
• The Investigator will attempt to establish a diagnosis of the event based on signs, symptoms, and/or other clinical information. Whenever possible, the diagnosis (not the individual signs/symptoms) will be documented as the AE/SAE.
 

Assessment of Intensity

The intensity of an AE is an estimate of the relative severity of the event made by the Investigator based on his or her clinical experience and familiarity with the literature. The following definitions are to be used to rate the severity of an AE:
 
 
• Mild: Asymptomatic or mild symptoms; clinical or diagnostic observations only; intervention not indicated.
 
• Moderate: Minimal, local, or noninvasive intervention indicated; limiting age-appropriate instrumental Activities of Daily Living (ADL). Instrumental ADL refers to preparing meals, shopping for groceries or clothes, using the telephone, managing money, etc.
 
• Severe: Severe or medically significant but not immediately life-threatening; hospitalization or prolongation of hospitalization indicated; disabling, limiting self-care ADL. Self-care ADL refers to bathing, dressing and undressing, feeding self, using the toilet, taking medications, and not bedridden.
 

Assessment of Causality

 
• The Investigator is obligated to assess the relationship between study intervention and each occurrence of each AE/SAE. The Investigator will use clinical judgment to determine the relationship.
 
• A reasonable possibility of a relationship conveys that there are facts, evidence, and/or arguments to suggest a causal relationship, rather than a relationship cannot be ruled out.
 
• Alternative causes, such as underlying disease(s), concomitant therapy, and other risk factors, as well as the temporal relationship of the event to study intervention administration, will be considered and investigated.
 

- For causality assessments, events assessed as having a reasonable possibility of being related to study intervention will be considered "related." Events assessed as having no reasonable possibility of being related to study intervention will be considered "unrelated."
- The Investigator will also consult the Investigator's Brochure and/or product information, for marketed products, in his/her assessment.
- For each AE/SAE, the Investigator **must** document in the medical notes that he/she has reviewed the AE/SAE and has provided an assessment of causality.
- There may be situations in which an SAE has occurred and the Investigator has minimal information to include in the initial report to the Sponsor or designee. However, it is very important that the Investigator always makes an assessment of causality for every event before the initial transmission of the SAE data to the Sponsor or designee.
- The Investigator may change his/her opinion of causality in light of follow-up information and send an SAE follow-up report with the updated causality assessment.
- The causality assessment is one of the criteria used when determining regulatory reporting requirements.

#### **Follow-up of AEs and SAEs**

- The Investigator is obligated to perform or arrange for the conduct of supplemental measurements and/or evaluations as medically indicated or as requested by the Sponsor or designee to elucidate the nature and/or causality of the AE or SAE as fully as possible. This may include additional laboratory tests or investigations, histopathological examinations, or consultation with other health care professionals.
- If a participant dies during participation in the study or during a recognized follow-up period, the Investigator will provide the Sponsor or designee with a copy of any postmortem findings including histopathology.
- New or updated information will be recorded in the originally submitted documents.
- The Investigator will submit any updated SAE data to the Sponsor or designee within 24 hours of the Investigator's awareness of the information.

#### **10.5.4 Reporting of SAEs**

##### **SAE Reporting to the Sponsor or Designee via an Electronic Data Collection System**

- The primary mechanism for reporting an SAE to the Sponsor or designee will be the electronic data collection system. The study site will enter the event into the electronic data collection system within 24 hours of the Investigator's awareness of the event.
- If the electronic system is unavailable, then the study site will use the paper SAE report form (see next section) to report the event and will enter the event into the electronic data collection system as soon as the system becomes available.
- After the study is completed at a given study site, the electronic data collection system will be taken offline to prevent the entry of new data or changes to existing data.
- If a study site receives a report of a new SAE from a study participant or receives updated data on a previously reported SAE after the electronic data collection system has been taken

offline, then the study site can report this information on a paper SAE report form (see next section) to the Sponsor or designee.

**SAE Reporting to the Sponsor or Designee via Paper SAE Report Form**

- The primary mechanism for reporting an SAE to the Sponsor or designee will be the paper SAE report form. The study site will submit the SAE report form, via email, within 24 hours of the Investigator's awareness of the event. Facsimile transmission may be utilized as an alternative mode of submission, if necessary.
- Notification of SAE information via telephone does not replace the need for the Investigator to complete, sign and submit the paper SAE report form to the Sponsor or designee within 24 hours of the Investigator's awareness of the event.

## 10.6 Appendix 6: Abbreviations and Definitions

Abbreviation	Definition
ACE	Angiotensin-converting enzyme
ADL	Activities of Daily Living
AE	Adverse event
AGA BETA BS	Agalsidase Beta Biosidus
ANMAT	The National Administration of Drugs, Foods and Medical Devices (Argentina)
Anti-AGA	Anti-agalsidase antibodies
ARBs	Angiotensin II receptor blockers
BPI-short form	Brief Pain Inventory short form
CFR	Code of Federal Regulations
CI	Confidence interval
COVID-19	Coronavirus disease 2019
ECG	Electrocardiogram
eCRF	Electronic case report form
eGFR	Estimated glomerular filtration rate
ERT	Enzyme replacement therapy
EU	European Union
FD	Fabry disease
FSH	Follicle-stimulating hormone
GCP	Good Clinical Practice
GL3 or Gb3	Globotriaocylceramide
HRT	Hormone replacement therapy
IARs	Infusion-associated reactions
ICF	Informed Consent Form
ICH	International Council for Harmonisation of Technical Requirements for Pharmaceuticals for Human Use
IEC	Independent Ethics Committee
IRB	Institutional Review Board
ITT	Intent To Treat
IV	Intravenous
Lyso-Gb3	Globotriaosylsphingosine

Abbreviation	Definition
PCT	Pharmacological chaperones
PD	Pharmacodynamics
PK	Pharmacokinetic
PP	Per Protocol
SAE	Serious adverse event
SAP	Statistical Analysis Plan
SD	Standard deviation
SF-36	36-Item Short Form Health Survey
SoA	Schedule of activities
US	United States
WOCBP	Women of childbearing potential
$\alpha$ -Gal A	$\alpha$ -galactosidase A

## MODIFICATION HISTORY

Unique Identifier for this Version	Date of the Document Version	Author	Significant Changes from Previous Authorized Version
1.0	08May2025	[name]	Not Applicable-First Version

---

Document: \\eedc-vnasc01\Biosdata\Biosidus\Agalsidase Beta\YZAA1358\Biostatistics\Documentation\SAP

Author: [name]

Version Number: V1.0

Version Date: 08May2025

Template No.: CS\_TP\_BS016 Revision 7

Reference: CS\_WI\_BS005

Effective Date: 01Nov2021

## LIST OF ABBREVIATIONS

Abbreviation	Term
ADL	Activities of Daily Living
AE	Adverse event
AGA BETA BS	Agalsidase Beta Biosidus
Anti-AGA	Anti-Agalsidase antibodies
BPI-short form	Brief Pain Inventory short form
CI	Confidence interval
COVID-19	Coronavirus disease 2019
ECG	Electrocardiogram
eCRF	Electronic case report form
IARs	Infusion-associated reactions
FD	Fabry disease
FSH	Follicle-stimulating hormone
ICF	Informed Consent Form
ITT	Intent to Treat
IV	Intravenous
PP	Per Protocol
SAE	Serious adverse event
SAP	Statistical Analysis Plan
SAF	Safety
SD	Standard deviation
Rand -36	36-Item Short Form Health Survey
SoA	Schedule of activities
WOCBP	Women of childbearing potential

Document: \\eedc-vnasc01\Biosdata\Biosidus\Agalsidase Beta\YZAA1358\Biostatistics\Documentation\SAP

Author: [name]

Version Number: V1.0

Version Date: 08May2025

Template No.: CS\_TP\_BS016 Revision 7

Reference: CS\_WI\_BS005

Effective Date: 01Nov2021

## 1. INTRODUCTION

This document describes the rules and conventions to be used in the presentation and analysis of Safety, Efficacy, and other relevant data for protocol BIO-AGA-Fase III-001. It describes the data to be summarized and analyzed, including specifics of the statistical analysis to be performed. This statistical analysis plan (SAP) is based on protocol version 6.0 dated 22APR2024.

## 2. OBJECTIVES AND ENDPOINTS

### 2.1 Primary Objective

The primary objective of the study is to evaluate the equivalence in efficacy between AGA BETA BS and Fabrazyme® after 6 months of treatment in patients with Fabry disease previously stabilized with Fabrazyme®, by measuring disease biomarker.

### 2.2 Secondary Objectives

- To evaluate the difference in efficacy between AGA BETA BS and Fabrazyme® after 1 year of treatment in patients with Fabry disease previously stabilized with Fabrazyme®, by measuring disease biomarker.
- To compare the pain severity before and after the treatment with AGA BETA BS in patients with Fabry disease previously stabilized with Fabrazyme®, as measured by the BPI-short form.
- To compare the impact of pain on daily functions before and after the treatment with AGA BETA BS in patients with Fabry disease previously stabilized with Fabrazyme®, as measured by the BPI-short form.
- To compare the patients' perception of their own health before and after the treatment with AGA BETA BS in patients with Fabry disease previously stabilized with Fabrazyme®, as measured by the Rand -36.

### 2.3 Exploratory Objective

Not Applicable

---

Document: \\needc-vnasc01\Biosdata\Biosidus\Agalsidase Beta\YZAA1358\Biostatistics\Documentation\SAP

Author: [name]

Version Number: V1.0

Version Date: 08May2025

Template No.: CS\_TP\_BS016 Revision 7

Reference: CS\_WI\_BS005

Effective Date: 01Nov2021

## 2.4 Safety Objectives

To characterize the safety of AGA BETA BS treatment in patients with Fabry disease previously stabilized with Fabrazyme®.

## 2.5 Primary Efficacy Endpoints & Derivation(s)

Mean Serum Lyso-Gb3 marker ratio after 26 weeks of treatment, defined as serum level of the marker Lyso-Gb3 after 26 weeks (6 months) divided by serum level of the marker Lyso-Gb3 at baseline.

## 2.6 Secondary Efficacy Endpoints & Derivations

- Mean serum Lyso-Gb3 marker ratio after 54 weeks of treatment, defined as serum level of the marker Lyso-Gb3 after 54 weeks (12 months) divided by serum level of the marker Lyso-Gb3 at baseline.
- Change from baseline in pain severity as assessed by BPI-short form pain severity items scores after 26 and 54 weeks of treatment.
- Change from baseline in pain interference as assessed by BPI-short form pain interference items scores after 26 and 54 weeks of treatment.
- Change from baseline in Rand -36 scores after 26 and 54 weeks of treatment.

## 2.7 Safety Endpoints & Derivations

- Evaluation of general health based on the analysis of laboratory values for hematology and clinical chemistry from blood samples collected at baseline and after 14, 26, and 54 weeks of treatment.
- Evaluation of renal function based on the analysis of laboratory values for BUN, eGFR, urine albumin-creatinine ratio, electrolytes, and phosphate, from blood and urine samples collected at baseline and after 14, 26, and 54 weeks of treatment.
- Evaluation of cardiac function based on the analysis of electrocardiogram and bidimensional echocardiogram exams performed at baseline and after 26 and 54 weeks of treatment.
- Evaluation of immunogenicity based on the analysis of anti-AGA levels from blood samples collected at baseline and after 14, 26, and 54 weeks of treatment.
- Analysis of data obtained from clinical and physical assessments, and from reported adverse events and infusion-related reactions throughout the clinical trial.

---

Document: \\needc-vnasc01\Biosdata\Biosidus\Agalsidase Beta\YZAA1358\Biostatistics\Documentation\SAP

Author: [name]

Version Number: V1.0

Version Date: 08May2025

Template No.: CS\_TP\_BS016 Revision 7

Reference: CS\_WI\_BS005

Effective Date: 01Nov2021

### 3 STUDY DESIGN

#### 3.1 General Description

BIO-AGA-Fase III-001 is a Phase III, prospective, multicenter, open-label, single-group, baseline-controlled, switch over clinical trial to evaluate the efficacy and safety of AGA BETA BS in patients with FD already treated and previously stabilized with Fabrazyme®.

The study will be conducted in 2 parts: a 5-week Lead-in period (period 1) and 54-week treatment period (period 2).

Details regarding Lead-in period and treatment period are provided below:

1. Lead-in period: all participants will receive 2 intravenous (IV) infusions of Fabrazyme®, provided by Biosidus, at a dose of 1 mg/kg of body mass, with 14 days between doses. The participant's baseline status will be assessed at the end of this period.
2. Treatment period: all participants will switch treatment to AGA BETA BS, administered at dose of 1 mg/kg of body mass, infused every 2 weeks as an IV infusion, for up to 54 weeks. Participants will receive a total of 27 infusions.

The design of this study is based on that used for the only biosimilar approved in an ICH member country (Japan). In both, a "patient's own historical control" is used as a control, in which the efficacy of AGA BETA BS is measured by comparing the value of the surrogate marker (Lyso-Gb3) at baseline - after at least 6 months of treatment with Fabrazyme® - compared to the value at 6 and 12 months of treatment with AGA BETA BS. This will be a paired comparison that maximizes the ability to detect variations in treatment efficacy.

##### **Number of Patients:**

A total of up to 20 patients are planned for the study. Patients will have previous diagnosis of FD, will be aged at least 18 years and no more than 60 years, will have received Fabrazyme® for at least 6 months, with treatment compliance of at least 80% of the prescribed dose during the last 3 months, and with disease status considered clinically stabilized, at the Investigators' discretion. At least 50% of the patients will be male with classic FD phenotype. The remaining percentage will consist of male late onset and classic women FD phenotype. Patients with chronic kidney disease in stage 3b, 4 or 5, who have suffered a clinical cardiovascular or cerebrovascular event in the last 6 months, who have acute kidney injury in the last 12 months or who have clinically significant unstable cardiac disease will be excluded from the trial.

##### **Intervention Groups and Duration:**

All patients will receive 2 doses of Fabrazyme® first, administered as an IV infusion at a dose of 1.0 mg/kg of body weight with 14 days between doses. After that, all patients will receive AGA

---

Document: \\eedc-vnasc01\Biosdata\Biosidus\Agalsidase Beta\YZAA1358\Biostatistics\Documentation\SAP

Author: [name]

Version Number: V1.0

Version Date: 08May2025

Template No.: CS\_TP\_BS016 Revision 7

Reference: CS\_WI\_BS005

[figure not shown]
Effective Date: 01Nov2021

BETA BS, administered at dose of 1 mg/kg of body weight, infused every 2 weeks as an IV infusion, for up to 54 weeks (27 infusions).

1. non-investigational prophylactic pretreatment with antihistamine will be administered at the Investigator's discretion to avoid infusion-associated reactions during the study, except during the first 2 infusions in period 2 in which administration will be compulsory. The antihistamine will be loratadine 10 mg, 1 to 2 hours before infusion, oral route. Furthermore, patients must remain in observation at the study center for at least 1 hour after each infusion during the first four AGA BETA BS infusions. In subsequent infusions, the center staff will contact each patient within 24 hours after infusion to check their clinical condition.

### Figure1: Study Design

**Figure 1 Study Schema**

AGA BETA BS=Agalsidase Beta Biosidus; FD=Fabry disease; IV=intravenous.

## 3.2 Schedule of Events

Schedule of events can be found in protocol section 1.3(Schedule of activities)

## 3.3 Changes to Analysis from Protocol

As per Latest protocol amendment (V6.0, dated 22 Apr2024), the data for Lyso-GB3 is collected from "Serum" instead of "Plasma". Thus, "Plasma" was expected to be replaced by "Serum" in

Document: \\eedc-vnasc01\Biosdata\Biosidus\Agalsidase Beta\YZAA1358\Biostatistics\Documentation\SAP

Author: [name]

Version Number: V1.0

Version Date: 08May2025

Template No.: CS\_TP\_BS016 Revision 7

Reference: CS\_WI\_BS005

Effective Date: 01Nov2021

all protocol. However, during protocol amendment in some sections this change was missed to be updated. Hence, all phrases suggesting "plasma" in TLF mock shells and SAP are modified to "Serum".

## 4 PLANNED ANALYSES

The following analyses will be performed for this study:

### 4.1 Sample Size Re-estimation (SSR)

A sample size re-estimation is planned to be carried out when 50% of the total number of participants is reached. The objective is to recalculate the sample size according to the pooled variability (% co-efficient of variation) observed so far.

- **Table 14.3.2.1.4:** Summary of Laboratory Values – Renal Function Parameters by Visit under Treatment Period (Safety Population)

### 4.3 Final Analysis

Final analysis will be performed when all active patients complete the Week 54 assessment visit. The efficacy endpoints up to week 54 and all available safety and efficacy data will be analyzed using the methods described in the analysis plan.

## 5 ANALYSIS POPULATIONS

Agreement and authorization of patients from Screened population included/excluded from each analysis Population will be conducted prior to the unblinding of the study.

### 5.1 Screened Population

Screened Population consists of all patients from screened population who provide informed consent for this study.

---

Document: \\needc-vnasc01\Biosdata\Biosidus\Agalsidase Beta\YZAA1358\Biostatistics\Documentation\SAP

Author: [name]

Version Number: V1.0

Version Date: 08May2025

Template No.: CS\_TP\_BS016 Revision 7

Reference: CS\_WI\_BS005

Effective Date: 01Nov2021

## 5.2 Enrolled Population (ENR)

Enrolled Population consists of all patients from screened population who meet all eligibility criteria for this study.

## 5.3 Intent To Treat Population (ITT)

Intent to Treat Population will include all patients from enrolled population who are part of the Lead-in period (Period 1). The ITT Population will be used for efficacy analyses.

## 5.4 Safety Population (SAF)

Safety Population will include all patients from ITT population who receive at least one dose of study treatment (AGA BETA BS). The Safety Population will be used for all safety analyses.

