### 9.2 Analysis Sets

For the purposes of analysis, the following analysis sets are defined:

**Intent To Treat (ITT) set:** Intent To Treat will include all participants who are part of the Lead-in period. The ITT population will be used for efficacy analyses.

**Safety Set:** Safety population will include all participants who receive at least one dose of study treatment (AGA BETA BS). The Safety population will be used for all safety analyses.

**Per Protocol (PP) set:** Per Protocol set will include all participants who satisfactorily complete the study and comply with the requirements of the protocol. It is a subset of the ITT population without any major protocol deviations. The PP population will be used for exploratory efficacy analyses. Final determinations of the PP population will be made at the data review meeting before database lock.

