## 14 STUDY MEDICATION EXPOSURE

Exposure to study Fabrazyme/ AGA BETA BS in weeks will be presented and summarized for the ITT population for Lead-in Period and Treatment Period respectively.

Duration of exposure (in weeks), no. of IP administrations, Number of patients exposed to IP week wise, Volume of dose administered will be summarized descriptively for Lead-in period and Treatment period.

Derivation for Duration of exposure is explained in section 14.1.

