## 17 SAFETY OUTCOMES

All outputs for safety outcomes will be based on the SAF population or ITT population. For Safety variables, formal statistical comparisons between treatment groups will not be performed.

---

Document: \\needc-vnasc01\Biosdata\Biosidus\Agalsidase Beta\YZAA1358\Biostatistics\Documentation\SAP

Author: [name]

Version Number: V1.0

Version Date: 08May2025

Template No.: CS\_TP\_BS016 Revision 7

Reference: CS\_WI\_BS005

Effective Date: 01Nov2021

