## 17.1 Adverse Events

All Adverse Events (AE) recorded in study will be coded using the MedDRA central coding dictionary version 25.1.

An AE will be defined as a treatment-emergent adverse event (TEAE) if they start on or after the date of the first dose of AGA BETA BS and would be counted only under treatment period and Non-TEAEs under Lead-in period in treatment period.

See [Appendix 1](#) for handling of partial dates for AEs. In the case where it is not possible to define an AE as treatment emergent or not, the AE will be classified by the worst case, i.e. treatment emergent.

Adverse events collected during the trial will be summarized by treatment groups and Period based on SAF population. Adverse events Listings will be presented for ITT population.

The number of AE and the number and percentage of patients experiencing AE will be summarized by severity and relationship to the Fabrazyme® and AGA BETA BS.

SAEs and AEs leading to premature study discontinuation will be summarized.

Listings will be provided for AEs based on severity and relationship to study medication.

Listings will be provided for AEs, SAE and AEs leading to discontinuation from study.

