### 17.1.1 All AEs

An overview of AE summary will be provided for both Lead-in period and Treatment period with the No. of events and n (%).

Following points will be considered in overview of AE

At least one

- AE
- Treatment related AE
- Severe AE
- Serious AE
- AE leading to discontinuation of study medication
- AE leading to Death
- Infusion Associated reactions
- Serious events
- AEs with maximum severity
- Relationship to Treatment (Study Medication)
- Action taken with AGA BETA BS and Fabrazyme®
- AEs by Outcome

Incidence of AEs will be presented by System Organ class (SOC) and Preferred Term (PT) and broken down further by maximum severity and relationship to study medication (AGA BETA BS) for Treatment period.

---

Document: \\needc-vnasc01\Biosdata\Biosidus\Agalsidase Beta\YZAA1358\Biostatistics\Documentation\SAP

Author: [name]

Version Number: V1.0

Version Date: 08May2025

Template No.: CS\_TP\_BS016 Revision 7

Reference: CS\_WI\_BS005

Effective Date: 01Nov2021

The number of patients with incidence of AE in two groups will be summarized and presented with frequency and percentage n (%) for Treatment period.

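### Lead-in AE summaries use a Safety Population that requires a later AGA BETA BS dose, so participants who stop or die on study Fabrazyme before the switch drop out of them

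*SAP*

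**What the plan says.** The two analysis sets differ exactly at the switch.

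- SAP 5.3 (ITT): "Intent to Treat Population will include all patients from enrolled population who are part of the Lead-in period (Period 1". Membership does not depend on going on to AGA BETA BS.
- SAP 5.4 (SAF): "Safety Population will include all patients from ITT population who receive at least one dose of study treatment (AGA BETA BS". Protocol 9.2 sets the same condition: "Safety population will include all participants who receive at least one dose of study treatment (AGA BETA BS". Both documents assign this set to all safety analyses, and Protocol 9.2.5 repeats it.

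For AE outputs, SAP 17 opens with a rule that does not choose: "All outputs for safety outcomes will be based on the SAF population or ITT population". SAP 17.1 does choose. For tables, "Adverse events collected during the trial will be summarized by treatment groups and Period based on SAF population"; for listings, "Adverse events Listings will be presented for ITT population".

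SAP 17.1.1 plans an AE overview, with event counts and n (%), for both periods. Its rows include serious AEs, infusion-associated reactions, AEs leading to death, and "AE leading to discontinuation of study medication". SAP 17.1 assigns an AE to a period by its start date relative to the first AGA BETA BS dose.

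Other Lead-in outputs use wider sets. For exposure, SAP 14 says: "Exposure to study Fabrazyme/ AGA BETA BS in weeks will be presented and summarized for the ITT population". Compliance (SAP 15) is also on ITT. Disposition (SAP 9.1) is presented for the screened population and counts participants who discontinue during the Lead-in.

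**The concern.** Whether a participant is counted in the Lead-in column depends on something that happens after the Lead-in: the first dose of the next product. The participants removed are those who did not get through the two study Fabrazyme infusions to the switch, and an AE is one reason for that. The overview nevertheless carries rows for AEs leading to discontinuation and to death in that period. Those rows invite the reader to take a low count as evidence about the reference product, when part of what they should count has been excluded by definition.

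Two further consequences follow. Lead-in AE percentages and Lead-in exposure and compliance can be reported with different N for the same period and product. And anyone who leaves before the switch for a reason other than an AE also drops out of the denominator, so the direction of the error for the any-AE row is not fixed. It is fixed only for events that themselves ended participation, which are always undercounted.

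Fabrazyme in the Lead-in is a sponsor-supplied study intervention (Protocol Table 4), and SAP 17.1 plans to summarise AEs by relationship to it. The column therefore needs a correct denominator even though it is descriptive.

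**Working it through.** There is no stated figure to reproduce; the point rests on set definitions. Protocol 7.1 moves a participant whose study intervention is permanently stopped to telephone follow-up, so a Lead-in stop means no AGA BETA BS dose.

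**Step 1. Routes by which a Lead-in-onset AE could reach the discontinuation row.**

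| Route | In ITT | In SAF | Counted in the row on SAF | Counted in the row on ITT |
|---|---|---|---|---|
| AE stops Fabrazyme, no AGA BETA BS dose | yes | no | no | yes |
| AE, participant switches, not stopped | yes | yes | no | no |
| AE, participant switches, AE later leads to stopping AGA BETA BS | yes | yes | yes | yes |

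Only the first route is lost. The same reasoning applies to deaths: a death before the switch is lost; a death after the switch from a Lead-in-onset AE is kept. In the first route all of the participant's other Lead-in AEs, serious AEs and infusion-associated reactions are lost as well.

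**Step 2. Size for an assumed number of pre-switch AE stops.** Let N = 20, the planned number (SAP 3.1), and assume that all 20 receive at least one study Fabrazyme infusion. Let k be the number who stop before the switch because of an AE, with no other pre-switch losses. The documents do not give k. The range 0 to 4 is an assumption; 4 equals the whole-study dropout allowance in Protocol 9.4 (0.20 × 20 = 4) and is an outer limit, not an expectation.

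- On SAF, the contribution to the row is 0/(N − k).
- On ITT, it is k/N.

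| k | SAF | ITT |
|---|---|---|
| 0 | 0/20 | 0/20 (0%) |
| 1 | 0/19 | 1/20 (5%) |
| 2 | 0/18 | 2/20 (10%) |
| 3 | 0/17 | 3/20 (15%) |
| 4 | 0/16 | 4/20 (20%) |

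**Step 3. Chance that the issue arises.** With an assumed risk p per participant of an AE stop before the switch, the chance of at least one in 20 is 1 − (1 − p)^20. For p = 1%, 2%, 5% and 10% this gives 18%, 33%, 64% and 88%. None of these values of p comes from the documents.

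**Step 4. Replacement.** Protocol 7.2 allows a participant withdrawn for an AE to be replaced and keeps the replaced participant's data. If one pre-switch AE withdrawal is replaced, ITT has 20 + 1 = 21 and SAF can still have 20. The SAF table would then show 0/20 where ITT gives 1/21 = 4.8%, and nothing in the AE table's N would signal the loss.

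**The case against.** The case for leaving this alone is substantial, and much of it stands.

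- **The participants are not lost from the report.** AE listings, AEs leading to death and deaths are on ITT (SAP 17.1, 17.1.4, 17.2), and SAP 9.1 tabulates Lead-in discontinuations with reasons. This stands. It does not correct the tabulated AE percentages.
- **The safety objective concerns AGA BETA BS, and no formal comparison is planned** (SAP 2.4, 17; Protocol 9.2.5). This stands. Two Fabrazyme infusions against 27 of AGA BETA BS would not be a balanced comparison on any set, and the plan also has change-from-baseline safety summaries. A reader might see the Lead-in column as the trial's only within-study safety contrast; the documents do not support that.
- **Tolerance of Fabrazyme is largely built in by eligibility**: at least 6 months of stable treatment and no history of type I hypersensitivity to agalsidase beta (Protocol 5.1, 5.2). This stands. The added conditioning comes only from two more infusions.
- **Pre-switch stops may be rare.** SAP 16.1 reports 11 ITT participants, all with Lyso-Gb3 data, and that sample is first scheduled at Baseline. This suggests little Lead-in attrition so far, but it is not proof, because Protocol Table 2 also collects Lyso-Gb3 at discontinuation.

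SAP 17's general wording does not rescue the plan. It names both sets without a rule, and SAP 17.1 then assigns SAF to the AE summaries. The table shells, which would show the actual column N, were not available for this check.

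**Conclusion.** The concern holds in a limited form. Under SAP 5.4 and 17.1, a participant who received study Fabrazyme and stopped or died before the switch is missing from both numerator and denominator of the Lead-in AE summaries, so an AE that stopped a participant before the switch cannot be counted there.

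Two stronger readings are tempting and do not hold. A reader might infer that the Lead-in rows for discontinuation and death must be zero; they need not be, because period follows AE start date and the third route in the working remains open. A reader might also infer that the AE percentages mix two sets; within the AE table both n and N are SAF, and the mismatch is between that table and the ITT-based exposure and compliance tables.

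The size depends on a count the documents do not give. With 1 or 2 pre-switch AE stops among 20, a true 5% or 10% would be tabulated as 0/19 or 0/18; with none, and no other pre-switch losses, nothing changes. The effect is confined to a descriptive column and does not touch the primary analysis or the Treatment-period AE results. It is still worth correcting, because the stated rule gives wrong percentages whenever such a loss occurs.

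**What to change.** 1. In SAP 17.1, base Lead-in AE columns on ITT participants who received at least one study Fabrazyme infusion, and keep SAF for Treatment-period columns.
2. Show both N values in the column headers.
3. In the opening of SAP 17, replace the choice between SAF and ITT with this rule.
4. Record the change in SAP 3.3, because Protocol 9.2 and 9.2.5 assign all safety analyses to the Safety Set.

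The cost is SAP wording, one entry in the list of changes from the protocol, and a different denominator in the Lead-in columns and their shells. No new data or procedures are needed, since the same participants are already in the ITT listings.
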